Full title:

A Multicenter Randomized Controlled Trial Assessing the Efficacy of Antimicrobial Prophylaxis for Extracorporeal Shock Wave Lithotripsy on Reducing Urinary Tract Infection

Brief Title:

Antibiotic Prophylaxis Before Shock Wave Lithotripsy (APPEAL)

1. Objectives & Specific Aims

The lifetime risk of developing nephrolithiasis has been reported between 1-15%, with a prevalence of approximately 5% in North America. SWL is a very common first line treatment for ureteral and renal calculi. One of its benefits is that it has few complications. However, infection remains an important complication of the procedure. Because of this risk the American Urological Association recommends pre-SWL antibiotics for all patients. However, this approach is controversial because studies to date are of poor quality and there is concern over antibiotic resistance. Therefore the European Association of Urology recommends only selective use of antibiotics pre-SWL. To resolve this conflict and establish the most appropriate strategy for Ontarians, we propose to perform a randomized trial comparing pre-procedure antibiotics to no antibiotics among patients who undergo SWL.

The primary goal of our study is to evaluate the impact of antibiotic prophylaxis on the rate of bacteriuria, symptomatic UTI, pyelonephritis and urosepsis among patients with sterile urine undergoing SWL. Our secondary goal is to determine pre-procedural characteristics that can define patient subgroups with the greatest benefit from prophylactic antibiotics.

We hypothesize that a single dose of intravenous ciprofloxacin immediately prior to SWL will decrease the relative incidence of bacteriuria, symptomatic UTI, pyelonephritis and urosepsis by 60% or greater. Additionally, we anticipate that pre-operative patient and stone characteristics such as age, gender, history of UTI, patient comorbidities, stone size, location, may be predictive risk factors that can be used to optimize patient selection for pre-operative antibiotic use.

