To test this hypothesis we propose to conduct a large ($n \geq 1350$), multicenter prospective randomized, blinded, placebo controlled trial (RCT). We recognize that our primary question may be difficult to study due to low rates of symptomatic UTI post-SWL. Therefore we propose to undertake this RCT in two phases. The Vanguard phase, which will consist of up to one fourth of the total study population, will be used to determine feasibility. Feasibility will be assessed in terms of rates of patient recruitment, percent adherence to randomization, percent data completion and percent loss to follow-up. Using pre-defined criteria, if the study is deemed to be feasible without major protocol alterations, the Vanguard phase patients will be included in the larger study. Patient recruitment will then continue until our target population size has been reached. Should the Vanguard phase be unable to demonstrate feasibility, then the available data will be analyzed, which will still provide the largest and most methodologically robust dataset available in the literature at this time.

The results of our RCT, whether positive or negative, will contribute significantly to the existing literature as it will provide the strongest Level 1 evidence available for future meta-analyses and guidelines. If the study results show a benefit to antibiotic use the expected impact on patient care will be to reduce rates of infectious complications. Furthermore, our study will allow for a more selective use of antibiotics as several important predictors of infectious complications will be elucidated through a multivariate analysis. Conversely, a null study will provide the strongest evidence against routine prophylaxis in the literature to date and potentially decrease the unnecessary use of antibiotics among patients undergoing SWL. Consequently, this would represent a cost savings to the healthcare system and may reduce the risk antibiotic resistant bacteria.

2. Background, Rationale & Present State of Knowledge

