- Taking antibiotics for UTI or other cause
- Suspected struvite stone (based on previous stone analysis, or partial staghorn)
- Presence of nephrostomy tube
- Requiring cystoscopy and ureteral stent insertion on the day of SWL
- Presence of Foley catheter or patient on regular clean intermittent catheterization (CIC)
- Presence of urinary diversion (ie: ileal conduit)
- History of urosepsis prior to SWL
- Known allergic reaction to trial antibiotic
- Previous randomization in this trial

Patients who are eligible for inclusion will then provide written informed consent. Risks and benefits will be discussed with the patient and will include being informed of a low risk of allergic reaction, colonization with antibiotic resistant organisms, and very low risk of developing of *C.Difficile* related diarrhea, or tendon injury. Conversely, the probability of successful SWL is not likely to be

influenced by our intervention. Participants will then fill out a pre-procedure study questionnaire in which baseline and demographic information will be gathered as well as a generic International Prostate Symptom Score (IPSS) questionnaire. Patients will be assigned a randomization number that will correspond to their treatment arm. Block randomization using blocks of 10 will be carried out by a central randomization organization (www.randomize.net) using a computerized algorithm. Only the research pharmacist at each site will have access to the randomization code, which will be made available for un-blinding once statistical analysis is complete. The patient and data analyst will remain blinded to treatment allocation. To ensure patient blinding, the IV solution will be concealed within a opaque paper bag or identical oral placebo and study medication will be manufactured.

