Data acquisition will be continuously monitored, with regular audits to assure that data from patients who have not complied with follow-up are obtained. Patients will be asked to provide a urine sample and complete and mail the follow-up form on post-operative day 7. If the follow-up questionnaire has not been received by post-operative day 10 patients will receive a reminder phone call. A second envelope will be sent containing a requisition for urine culture and follow-up questionnaire when necessary.

Our primary outcome will be a composite endpoint comprised of:

- Positive post-SWL urine culture ($\geq 10^5$ CFU/ ml), symptoms of cystitis (defined as new onset burning sensation or pain with voiding, frequency, urgency), or pyelonephritis or urosepsis (hospital admission with fever ≥ 38.5 C).

Our secondary outcomes will be:

Version 8.1 Last modified August 21, 2018

- Bacteriuria at 7-14 days post-SWL ($\geq 10^5$ cfu/ml)
- Symptoms of cystitis (new onset burning sensation or pain with voiding, frequency, urgency)
- Pyelonephritis or urosepsis (hospital admission with fever $\geq 38.5^\circ\text{C}$)
- Change in IPSS score at 2 weeks (reported as a numerical value)

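### No outcome or planned analysis compares drug harms or antibiotic resistance by arm, although resistance is one of two reasons given for the controversy and four drug risks are disclosed at consent

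*Combined protocol and SAP*

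**What the plan says.** Section 1 (Objectives & Specific Aims) explains why routine prophylaxis is disputed: "this approach is controversial because studies to date are of poor quality and there is concern over antibiotic resistance". It later describes what a null result would mean for practice: "this would represent a cost savings to the healthcare system and may reduce the risk antibiotic resistant bacteria".

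The consent paragraph in section 4 (Project Design, Methodology and Analysis) has patients "informed of a low risk of allergic reaction, colonization with antibiotic resistant organisms", and it goes on to C. difficile "related diarrhea, or tendon injury". These risks are described there as low or very low.

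The outcome lists come later in section 4. The first opens "Our primary outcome will be a composite endpoint comprised of" and covers positive culture, cystitis symptoms, and pyelonephritis or urosepsis. The second opens "Our secondary outcomes will be" and gives the same components separately, plus change in IPSS. Under Statistical analysis, the plan undertakes to report baseline characteristics and these primary and secondary outcomes. Nowhere does it describe collecting adverse events, testing susceptibility or comparing any harm between arms.

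**The concern.** The trial is meant to resolve a conflict between two guidelines on whether an antibiotic should be given to all patients with sterile urine. That decision has two sides, and the plan measures one. If ciprofloxacin reduces the composite, the report would favour routine use with no planned randomized comparison of the four risks that participants were told about. If it does not, the statement that less prophylaxis may reduce resistance would rest on no trial data. Harm questions that are not asked during follow-up cannot be reliably recovered afterwards, so this has to be settled before data collection.

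**Working it through.** **1. The plan's own sample size.** Inputs from Power and sample size calculation: 5.7% against 2.1%, 90% power, significance level 0.05. Sidedness is not stated; two-sided is assumed. The mean rate is 0.039 and the difference 0.036.

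- Uncorrected: n = [1.96·√(2·0.039·0.961) + 1.2816·√(0.057·0.943 + 0.021·0.979)]² / 0.036² = 606 per arm.
- With continuity correction: (n/4)·[1 + √(1 + 4/(n·0.036))]² = 661 per arm.

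The stated 661 reproduces exactly. Descriptive safety outcomes would not change it.

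**2. Risks disclosed against outcomes planned.**

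- Allergic reaction: no outcome, no analysis.
- Colonization with resistant organisms: no outcome, no analysis.
- C. difficile diarrhea: no outcome, no analysis.
- Tendon injury: no outcome, no analysis.

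**3. What the post-SWL culture could yield on resistance.** The target of 1350 patients with complete data gives 675 per arm.

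- Placebo: 675 × 0.057 = 38.5 positive cultures.
- Ciprofloxacin: 675 × 0.021 = 14.2.
- Total: 52.65, about 53.

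The documents give no resistant share, so a range is assumed. With r the share, the 95% half-width is 1.96·√(r(1−r)/m), using m = 38 and m = 14. For the difference it is 1.96·√(r(1−r)(1/38 + 1/14)).

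| Assumed share | Placebo | Ciprofloxacin | Difference |
|---|---|---|---|
| 10% | 10 points | 16 points | 18 points |
| 20% | 13 points | 21 points | 25 points |
| 50% | 16 points | 26 points | 31 points |

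Approximate power to compare shares among isolates is 32% for 20% against 40%, and 79% for 20% against 60%.

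**4. Why one resistance measure is not enough.** Suppose the resistant share is 20% on placebo and doubles to 40% on ciprofloxacin (assumed). Resistant positives per patient are then:

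- Placebo: 0.057 × 0.20 = 1.14%.
- Ciprofloxacin: 0.021 × 0.40 = 0.84%.

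This measure favours the antibiotic even though the share doubled, because total bacteriuria fell. The share among isolates shows the doubling, but it compares subsets formed after randomization.

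**5. What the follow-up form could yield on harms.** With no events in 675 patients, the upper limit is 1 − 0.05^(1/675) = 0.44% (one-sided 95%) or 1 − 0.025^(1/675) = 0.55% (two-sided 95%). The chance of seeing at least one event is 1 − (1 − q)^675, which is 49% at a true rate of 0.1% and 97% at 0.5%. Power is about 33% for 1% against 2%, and 75% for 1% against 3%. All harm rates here are assumptions; the documents give none.

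**6. Missing forms.** The Statistical analysis section counts patients lost to follow-up as event-free. If that rule were carried over to harms with 10% lost, a rate h among responders would be reported as 0.9h.

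**The case against.** The strongest reply is that the plan sets out to measure efficacy, that its efficacy aims are intact, and that the available material could not settle harm or resistance anyway. Much of this stands. About 53 isolates and 675 patients per arm support description, not a powered comparison. A single urine culture at 7–14 days does not measure colonization elsewhere in the body, and a form due around day 7 may miss later events.

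A reader might also infer three things that the documents do not support.

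- **That drug harms are the stated reason for doubting prophylaxis.** Section 1 gives two reasons, poor-quality studies and resistance. The other drug risks appear only as consent information.
- **That the needed data already flow through existing forms and cultures.** The channels exist, but no text says that laboratories report susceptibility, and section 4 accepts that culture protocols differ between laboratories. The only questionnaire content described is baseline and demographic information, urinary symptoms and IPSS.
- **That no harm will be recorded at all.** The forms are not reproduced in the document, so harm items on them cannot be excluded.

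None of this removes the omission. The outcome lists and the analysis section are present, and neither plans a comparison of harm or resistance by arm.

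**Conclusion.** The concern holds in a limited form. Nothing in the outcomes or the analysis plan compares harms or resistance between arms, so the evidence from the trial would be one-sided and its remark on resistance unsupported. The primary analysis and the 661 per arm are not affected.

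A reader might infer that adding these outcomes would let the trial weigh benefit against harm with confidence. It would not: it would replace no planned information with wide but honest intervals. The isolate count assumes the plan's bacteriuria rates and 675 cultured patients per arm. The 0.44% and 0.55% limits assume complete and accurate harm reporting in all 675. The change is worth making because it is cheap and bears on the trial's stated purpose; it is not a flaw that invalidates the design.

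**What to change.** Add two safety outcomes to the secondary list in section 4, stated to be descriptive and unpowered. Add their analysis by arm, with confidence intervals (exact ones, given the small counts), to Statistical analysis.

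1. **Harms.** Ask about allergic reaction, diarrhea or a C. difficile diagnosis, and tendon symptoms on the existing follow-up form. Analyse patients who returned the form, show the number without one in each arm, and do not treat lost patients as event-free.
2. **Resistance.** Record ciprofloxacin susceptibility for each positive post-SWL culture where the laboratory reports it. Give both resistant positives per randomized patient and the resistant share among isolates, with the number of missing results.

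State four limits beside the table:

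- The share among isolates is a post-randomization subset.
- The per-patient measure can fall simply because bacteriuria falls.
- Urine culture does not capture colonization elsewhere.
- One early form may miss later events.

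The cost is a slightly longer form, one data field per positive culture, one extra table, and susceptibility data that will be incomplete. The sample size does not change. The change does not create interim safety monitoring, which would need its own provision.

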The proposed study will be carried out in two phases. The initial Vanguard phase will assess the feasibility of the trial in terms of rates of patient recruitment, percent adherence to randomization, percent data completion and percent loss to follow-up. Pre-defined criteria to determine feasibility will be a rate of randomization of ≥ 16 patients per week, with 95% adherence to randomization and an overall rate of $\geq 90\%$ data collection at 3 weeks post-SWL, and an overall loss to follow-up of $\leq 10\%$. These parameters will be assessed weekly throughout the Vanguard period. This phase of the study will continue until all target parameters have been met for 3 consecutive weeks and a minimum of 200 patients have been randomized. If these parameters are met then the Vanguard phase will be interpreted to have demonstrated feasibility and patient recruitment will continue until complete data for ≥ 1350 patients has been collected. Alternatively, the Vanguard phase may be concluded when a maximum of 300 patients or a six month period from study start date has elapsed or a modification to number of sites accruing may be considered. If the Vanguard phase fails to demonstrate feasibility, and we judge that this indicates that a significant protocol modification is needed we will close the trial and analyze available data. The data would be analyzed in accordance with pre-defined methodology and would be submitted for publication. Importantly, even if the Vanguard phase does not show feasibility, it would still provide the largest cohort of high quality data available in the literature and as such would still be an important contribution to the current state of knowledge.

The study centres, Helsinki University Hospital, University of Western Ontario St Joseph's Hospital, Université de Sherbrooke, Pontifical University Catholic of Campinas, Rede D'Or Sao Luiz, and King Abdulaziz University are each academic institutions with dedicated research staff. We estimate that total of 2000 patients will need to be screened in order to acquire complete data for 1350 patients. Accounting for a 10% dropout, up to 1500 patients may need to be randomized. Eligibility criteria include patients older than 18 years presenting for SWL who do not meet one of the pre-defined exclusion criteria. Exclusion criteria are:

- Pre-SWL urine analysis positive for nitrites
- Pre-SWL urine culture reveals $>10^5$ CFU/ml of bacteria (positive urine culture)

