Patients routinely undergo neuroleptic anesthesia during SWL at participating centers, as such it is usual care for the patient to have a saline infusion during SWL. The choice of whether or not to administer antibiotics is usually at the discretion of the attending urologist, as there is no established standard of care. For the duration of the study, participants will be mandated to receive treatment in accord with randomization. However the attending urologist will retain the ability to break protocol in accord with their clinical judgment. Any break in protocol will be recorded as such but the data will be analyzed on an intent-to-treat basis. Ciprofloxacin was chosen as the study antibiotic as it is commonly used in everyday practice, has been used in previous RCTs on antibiotic prophylaxis pre-SWL³¹ and demonstrates a good sensitivity pattern to community acquired infections. Patients will undergo SWL with a maximum of 3000 shock waves (SW) for kidney stones and up to 4500SW for ureteric stones. Additional clinical parameters such as presence of double J, Stone characteristics and renal insufficiency will be recorded at the time of SWL by the dedicated research staff.

Patients will be asked to provide two urine samples for analysis. The first will be prior to SWL within 1 month of the procedure. On the day of procedure the patient will also complete baseline documentation. After the procedure, patients will complete follow-up documentation and a second urine culture. Urine cultures will be submitted to the laboratory or hospital most convenient for the patient at 7-14 days post-SWL and results will be forwarded to the regional site. We allow the patient to submit a urine culture at their usual laboratory in an effort to minimize the burden for the patient participating in the trial and to facilitate capture of follow-up data. This approach may be essential to capture data from patients referred from an outside institution, which may represent a significant commute. An additional advantage of this approach, in contrast to mandating the use of a central laboratory, is that it may better reflect the usual pattern of patient behavior when seeking follow-up for urinary tract symptoms post-SWL. We recognize that there may be differences in culture protocol between laboratories but we feel that these are more representative of actual practice and as such support the generalizability of the study.

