The power calculation for this protocol was performed using Stata v.10.1 (StataCorp, College Station, TX). Reported incidence of bacteriuria, symptomatic UTI and pyelonephritis post-SWL vary greatly¹⁰⁻¹³. Therefore, to estimate the expected incidence of our primary outcome, we used the incidence of bacteriuria reported in the AUA Best Practice Statement on antibiotic prophylaxis¹⁷. In the AUA statement, patients undergoing SWL in the placebo arm of trials assessing antibiotic prophylaxis had a 5.7% rate of bacteriuria as compared to 2.1% among those who received prophylaxis. This represented an absolute difference of 3.6% (a 60% relative risk reduction). Therefore to achieve a power of 90% to find an absolute difference of 3.6% in the occurrence of bacteriuria, with a significance level of $p < 0.05$, 661 patients will need to be recruited in each arm for a total of 1,322 patients. Accounting for 10% loss to follow-up, the total required will be 1454, or approximately 1500 patients. Assuming that 25% of patients screened will either refuse to be randomized or will meet one of the pre-defined exclusion criteria, a total of 2000 patients will need to be screened in order to randomize 1500 patients.

Statistical analysis

Once all study data has been collected, we will report the patient characteristics at enrollment, and the primary and secondary outcomes. Comparison between RCT outcomes will be performed using Fisher's exact test for binary outcomes and Student's t-test for continuous outcomes. Lost to follow-up will be accounted for according to intent to treat analysis. Patients who are lost to follow-up will be considered not to have bacteriuria, cystitis, pyelonephritis or urosepsis and a change in IPSS of zero. This will allow us to accomplish the primary objective: to determine the impact of antibiotic prophylaxis on our primary and pre-defined secondary endpoints. We will also perform a univariate and multivariate analysis using a stepwise logistic regression model to assess predictors of our primary

outcome. This will allow us to better characterize the impact of pre-SWL antibiotic use in the context of other known risk factors for UTI.

Strengths and weaknesses of study design

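### The primary test is a pooled Fisher's exact test with no site term, and no site stratification is stated; a site-stratified Cochran-Mantel-Haenszel test would be a cheap, minor gain

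*Combined protocol and SAP*

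**What the plan says.** Section 4 (Project Design, Methodology and Analysis) states: "Block randomization using blocks of 10 will be carried out by a central randomization organization". No stratification factor and no second block size are mentioned. The same paragraph adds: "Only the research pharmacist at each site will have access to the randomization code". Section 4 lists six study centres.

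Under Statistical analysis: "Comparison between RCT outcomes will be performed using Fisher's exact test for binary outcomes". The primary composite is binary, so this is the primary test. No site term, effect measure or confidence interval is specified. The only regression is a "univariate and multivariate analysis using a stepwise logistic regression model to assess predictors of our primary" outcome, and site is not named among its covariates.

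On urine cultures, section 4 says: "We recognize that there may be differences in culture protocol between laboratories". It accepts these differences as reflecting ordinary practice and lets each patient use a convenient laboratory.

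**The concern.** The plan expects culture methods to differ between laboratories and recruits at six centres, so the chance of counting as an event may differ by site. If allocation is not balanced within site, the arms can differ by chance in site mix. If allocation is balanced within site, the analysis leaves out a design factor. Either way, the primary test cannot use site information, and Fisher's exact test rejects less often than its nominal 5% level allows. What is at stake is precision and a clear specification, not the validity of the comparison.

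**Working it through.** **1. The plan's own sample size.** Inputs from Power and sample size calculation: 5.7% versus 2.1%, power 90%, significance level 0.05 (taken as two-sided). With p̄ = (0.057 + 0.021)/2 = 0.039:

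n = [1.960·√(2·0.039·0.961) + 1.282·√(0.057·0.943 + 0.021·0.979)]² / 0.036² = (0.5366 + 0.3493)² / 0.001296 ≈ 605.6, so 606 per arm.

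With continuity correction: (605.6/4)·[1 + √(1 + 4/(605.6·0.036))]² = 151.4 · 2.0879² ≈ 660.03, so 661 per arm. This matches the plan. The correction means that the sample size already allows for most of Fisher's conservatism.

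**2. Fisher's test with no site effect.** Full enumeration of two binomials, against an uncorrected Pearson chi-square test:

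| Per arm | Rates | Fisher | Pearson |
|---|---|---|---|
| 661 | 5.7% v 2.1% | 91.7% | 93.5% |
| 661 | 5.7% v 2.85% (50% reduction) | 69.1% | 73.7% |
| 675 | 5.7% v 2.1% | 92.0% | 94.0% |
| 675 | 5.7% v 2.85% | 69.9% | 74.6% |

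At 661 per arm, with a common rate between 2.1% and 5.7%, Fisher's true size is 3.3% to 3.8%; Pearson's is about 5%. Changing the test alone is therefore worth about 2 points at the planned effect and about 5 at a 50% reduction, with no site difference present.

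**3. Adding site differences (simulation).** The CMH statistic was used without continuity correction: Σ(y₁ₖ − tₖn₁ₖ/nₖ), divided by the square root of Σ n₁ₖn₀ₖtₖ(nₖ − tₖ)/[nₖ²(nₖ − 1)], summed over sites k. Here y₁ₖ is the events on active treatment, tₖ all events, n₁ₖ and n₀ₖ the arm sizes, and nₖ their total. Site sizes and site rates are assumptions, because the documents give none.

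| Setting | Allocation | Fisher | Pearson | CMH |
|---|---|---|---|---|
| A: 1,322 patients, equal sites, control rates about 1% to 11% (mean 5.7%), 63% reduction | unstratified | 92.5% | 94.0% | 93.9% |
| | stratified | 92.9% | 93.9% | 94.0% |
| B: 1,350 patients, sites 400/300/250/200/150/50, control rates about 3.3% to 10.8% (mean 5.7%), 63% reduction | unstratified | 91.9% | 94.0% | 93.8% |
| | stratified | 91.7% | 93.8% | 93.8% |
| C: as B, 50% reduction | unstratified | 69.8% | 74.6% | 74.8% |
| | stratified | 70.0% | 74.9% | 75.0% |
| D: 1,322 patients, equal sites, control rates 10% to 50% (mean 30%), 22.6% on treatment | unstratified | 84.8% | 86.2% | 89.5% |
| | stratified | 86.7% | 87.5% | 89.2% |

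In A to C, CMH equals Pearson within simulation error, and stratified allocation adds nothing detectable. In A, site explains only about 2.3% of the outcome variance. In D it explains about 8.9%, and CMH gains 1.7 to 3.3 points over Pearson; a separate run with slightly different inputs gave 2.4.

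**4. Type I error.** Fisher's simulated size ran from 3.4% to 4.7%, with a standard error of about 0.3 points at 5,000 trials; about 3.3% to 4.5% summarises the exact and simulated figures. CMH ran from 4.6% to 5.8%. The 5.8% came from one 5,000-trial run, and 8,000 trials of the same design gave 4.9%. No test showed real inflation.

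**5. Chance imbalance if blocks are not site-specific.** With six equal sites of about 220, the mean departure from 50:50 is about 2.5 percentage points and the 95th percentile about 6, against 0.2 and 0.7 if stratified. At a site of about 66 patients the 95th percentile is about 12 points, against about 2. With the site sizes and rates of B, this moves the expected control-rate difference between arms by about 0.1 percentage point on average, against a planned 3.6.

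**The case against.** The strongest reply is that the planned test does its job. The sample size was computed with a continuity correction, Fisher's test exceeds 90% power at the planning rates, and its type I error stays below 5%. A 50% reduction is smaller than the 60% or more that the trial hypothesizes. Chance imbalance by site is ordinary random variation that the test already covers. The plan also considers laboratory variation and accepts it, and because patients choose the laboratory, site is only a partial proxy for it. All of this stands, and it limits the weight of the point.

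Three stronger readings are tempting, and the documents do not support them.

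- A reader might infer that randomization is unstratified. The plan is silent, and a code held by the pharmacist at each site is compatible with site-specific lists.
- A reader might infer that ignoring site costs power. At 5.7% versus 2.1% it does not; Pearson's test ignores site too and matches CMH.
- A reader might infer from setting D that the trial is underpowered. The 5.7% is a bacteriuria rate, and the composite also counts symptoms that stone debris or a stent can cause, so its rate could well be higher. But neither 30% nor the 10% to 50% spread between sites is in the documents.

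What the reply does not remove is that the plan leaves the allocation scheme unclear, gives no effect estimate or interval, and uses a test that gives up some power without need.

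**Conclusion.** The point holds as a cheap improvement of minor weight. It shows no bias, no inflated error rate and no shortfall against the stated 90% power.

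Replacing the pooled Fisher's test with a site-stratified CMH test recovers about 2 points of power at the planned effect and about 5 at a 50% reduction, with type I error near 5%. At the planning rates essentially all of this comes from leaving Fisher's test. The part due to site, about 2 to 3 points, depends on an assumed composite rate near 30% and wide differences between sites.

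The Fisher power and size at the planning rates are exact. The site results rest on assumed site sizes and rates.

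**What to change.** 1. **Allocation.** State that the central randomization is stratified by site, with randomly varied block sizes. Site-level blocks of one known size would be easier to predict locally, and varied sizes offset that. If allocation has begun, leave it as it is, document whether blocks were site-specific, and change only the analysis, before unblinding.
2. **Primary analysis.** Use a CMH test stratified by site, specified without continuity correction as in the calculations above, and report a site-adjusted risk difference or risk ratio with 95% CI.
3. **Small sites.** Pre-specify a rule for pooling very small sites, fixed before unblinding.
4. **Sensitivity.** Keep Fisher's exact test as a sensitivity analysis.

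The cost is a setting in the randomization system and a few sentences in the SAP. There are small downsides: a site with no events adds nothing to the stratified test, CMH is asymptotic rather than exact, and stratifying by site captures laboratory differences only in part.
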